- HVTN scientists and operational staff incorporate the philosophies underlying major codes (1-3), declarations, and other guidance documents relevant to human subjects research into the design and conduct of HIV vaccine clinical trials.
- HVTN scientists and operational staff are committed to substantive community input—into the planning, conduct, and follow-up of its research—to help ensure that locally appropriate cultural and linguistic needs of study populations are met. Community Advisory Boards (CAB) are required by DAIDS and supported at all HVTN research sites to ensure community input.
- HVTN clinical trial staff counsel study participants routinely on how to reduce HIV risk. Participants who become HIV-infected during the trial are provided counseling on notifying their partners and about HIV infection according to local guidelines. Staff members will also counsel them about reducing their risk of transmitting HIV to others.
- Participants who become HIV-infected during the trial are referred to medical practitioners to manage their HIV infection and to identify potential clinical trials they may want to join. If a program for antiretroviral therapy (ART) provision is not available at a site and ART is needed, a privately established fund will be used to pay for access to treatment to the fullest extent possible.
- The HVTN provides training so that all participating sites similarly ensure fair participant selection, protect the privacy of research participants, and obtain meaningful informed consent. During the study, participants will have their wellbeing monitored, and to the fullest extent possible, their privacy protected. Participants may withdraw from the study at any time.
- Prior to implementation, HVTN trials are rigorously reviewed by scientists who are not involved in the conduct of the trials under consideration.

- HVTN trials are reviewed by local and national regulatory bodies and are conducted in compliance with all applicable national and local regulations.
- The HVTN designs its research to minimize risk and maximize benefit to both study participants and their local communities. For example, HVTN protocols provide enhancement of participants' knowledge of HIV and HIV prevention, as well as counseling, guidance, and assistance with any social impacts that may result from research participation. HVTN protocols also include careful medical review of each research participant's health conditions and reactions to study products while in the study.
- HVTN research aims to benefit local communities by directly addressing the health and HIV prevention needs of those communities and by strengthening the capacity of the communities through training, support, shared knowledge, and equipment. Researchers involved in HVTN trials are able to conduct other critical research in their local research settings.
- The HVTN values the role of in-country Institutional Review Boards (IRBs), Ethics Committees (ECs), and other Regulatory Entities (REs) as custodians responsible for ensuring the ethical conduct of research in each setting.

2 IRB/EC review considerations

US Food and Drug Administration (FDA) and other US federal regulations require IRBs/ECs/REs to ensure that certain requirements are satisfied on initial and continuing review of research (Title 45, Code of Federal Regulations (CFR), Part 46.111(a) 1-7; 21 CFR 56.111(a) 1-7). The following section highlights how this protocol addresses each of these research requirements. Each HVTN Investigator welcomes IRB/EC/RE questions or concerns regarding these research requirements.

2.1 Minimized risks to participants

45 CFR 46.111 (a) 1 and 21 CFR 56.111 (a) 1: Risks to subjects are minimized.

This protocol minimizes risks to participants by (a) correctly and promptly informing participants about risks so that they can join in partnership with the researcher in recognizing and reporting harms; (b) respecting local/national blood draw limits; (c) performing direct observation of participants postvaccination and collecting information regarding side effects for several days postvaccination; (d) having staff properly trained in administering study procedures that may cause physical harm or psychological distress, such as blood draws, vaccinations, HIV testing and counseling and HIV risk reduction counseling; (e) providing HIV risk reduction counseling and checking on contraception use (for persons assigned female at birth); and (f) providing safety monitoring.

2.2 Reasonable risk/benefit balance

45 CFR 46.111(a) 2 and 21 CFR 56.111(a) 2: Risks to subjects are reasonable in relation to anticipated benefits, if any, to subjects, and the importance of the knowledge that may reasonably be expected to result.

In all public health research, the risk-benefit ratio may be difficult to assess because the benefits to a healthy participant are not as apparent as they would be in treatment protocols, where a study participant may be ill and may have exhausted all conventional treatment options. However, this protocol is designed to minimize the risks to participants while maximizing the potential value of the knowledge it is designed to generate.

2.3 Equitable participant selection

45 CFR 46.111 (a) 3 and 21 CFR 56.111 (a) 3: Subject selection is equitable

This protocol has specific inclusion and exclusion criteria for investigators to follow in admitting participants into the protocol. Participants are selected because of these criteria and not because of positions of vulnerability or privilege. Investigators are required to maintain screening and enrollment logs to document volunteers who screened into and out of the protocol and for what reasons.

2.4 Appropriate informed consent

45 CFR 46.111 (a) 4 and 5 and 21 CFR 56.111 (a) 4 and 5: Informed consent is sought from each prospective subject or the subject's legally authorized representative as required by 45 CFR 46.116 and 21 CFR Part 50; informed consent is appropriately documented as required by 45 CFR 46.117 and 21 CFR 50.27

The protocol specifies that informed consent must be obtained before any study procedures are initiated and assessed throughout the trial (see Section 9.1). Each site is provided training in informed consent by the HVTN as part of its entering the HVTN. The HVTN requires a signed consent document for documentation, in addition to chart notes or a consent checklist.

2.5 Adequate safety monitoring

45 CFR 46.111 (a) 6 and 21 CFR 56.111 (a) 6: There is adequate provision for monitoring the data collected to ensure the safety of subjects.

This protocol has extensive safety monitoring in place (see Section 9). Safety is monitored daily by HVTN Core and routinely by the HVTN 133 Protocol Safety Review Team (PSRT). In addition, the HVTN Safety Monitoring Board (SMB) periodically reviews study data.

2.6 Protect privacy/confidentiality

45 CFR 46.111 (a) 7 and 21 CFR 56.111 (a) 7: There are adequate provisions to protect the privacy of subjects and maintain the confidentiality of data.

Privacy refers to an individual's right to be free from unauthorized or unreasonable intrusion into his/her private life and the right to control access to individually identifiable information about him/her. The term "privacy" concerns

research participants or potential research participants as individuals whereas the term “confidentiality” is used to refer to the treatment of information about those individuals. This protocol respects the privacy of participants by informing them about who will have access to their personal information and study data (see [Appendix A](#)). The privacy of participants is protected by assigning unique identifiers in place of the participant’s name on study data and specimens. In the United States, research participants in HVTN protocols are protected by a Certificate of Confidentiality from the US NIH, which can prevent disclosure of study participation even when that information is requested by subpoena. Participants are told of the use and limits of the certificate in the study consent form. In addition, each staff member at each study site in this protocol signs an Agreement on Confidentiality and Use of Data and Specimens with the HVTN. In some cases, a comparable confidentiality agreement process may be acceptable. Each study site participating in the protocol is required to have a standard operating procedure on how the staff members will protect the confidentiality of study participants.

3 Overview

Title

A phase 1 clinical trial to evaluate the safety and immunogenicity of an HIV-1 gp41 MPER-656 liposome vaccine in healthy, HIV-uninfected adult participants

Primary objective(s)

Primary objective 1

- To evaluate the safety and tolerability of different doses of a prime-boost regimen of MPER-656 liposomes in HIV-uninfected healthy adults

Primary endpoint 1

- Local and systemic reactogenicity signs and symptoms, laboratory measures of safety, and adverse events (AEs) and serious adverse event (SAEs)

Primary objective 2

- To evaluate binding antibody responses elicited by different doses of the MPER-656 liposome vaccine

Primary endpoint 2

- MPER-peptide-specific immunoglobulin G (IgG) binding antibody (Ab) responses as assessed by binding Ab multiplex assay 2 weeks after the 3rd and 4th vaccination with MPER-656 liposome vaccine

Study products and routes of administration

- MPER-656 liposomes at 0.5 mg/mL with 500 mcg alum (from 5 mg/mL suspension) for two 0.5 mL doses in two sites (total dose of 500 mcg in 1 mL) administered by IM injection in the deltoid muscles (one injection into each deltoid)
- MPER-656 liposomes at 2 mg/mL with 500 mcg alum (from 5 mg/mL suspension) for two 0.5 mL doses in two sites (total dose of 2000 mcg in 1 mL) administered by IM injection in the deltoid muscles (one injection into each deltoid)
- Sodium Chloride for Injection USP, 0.9% administered for two 0.5 mL doses in two sites by IM injection in the deltoid muscles (one injection into each deltoid)

Table 3-1 Schema

Study arm	N	Month 0 (Day 0)	Month 2 (Day 56)	Month 6 (Day 168)	Month 12 (Day 364)
Group 1	5	500 mcg peptide	500 mcg peptide	500 mcg peptide	500 mcg peptide
	1	Placebo	placebo	placebo	placebo
Group 2	15	2000 mcg peptide	2000 mcg peptide	2000 mcg peptide	2000 mcg peptide
	3	Placebo	placebo	placebo	placebo
Total	24 (20/4)				

Note:

Safety data for Group 1 through 2 weeks after the first vaccination will inform whether to proceed with escalation to the higher dose (Group 2).

Participants

24 healthy, HIV-1–uninfected volunteers aged 18 to 50 years; 20 vaccinees, 4 placebo recipients

Design

Multicenter, randomized, dose escalation, placebo-controlled, double-blind trial

Duration per participant

18 months of scheduled clinic visits per participant (main study), followed by an adverse event of special interest (AESI) health contact at month 24

Estimated total study duration

30 months (includes enrollment, planned safety holds, follow-up, and AESI health contact)

Investigational New Drug (IND) sponsor

DAIDS, NIAID, NIH, DHHS (Bethesda, Maryland, USA)

Study product provider

- MPER-656 liposomes: International AIDS Vaccine Initiative, (IAVI, New York, New York, USA)

Core operations

HVTN Vaccine Leadership Group/Core Operations Center, Fred Hutchinson Cancer Research Center (Fred Hutch) (Seattle, Washington, USA)

Statistical and data management center (SDMC)

Statistical Center for HIV/AIDS Research and Prevention (SCHARP), Fred Hutch (Seattle, Washington, USA)

HIV diagnostic laboratory

University of Washington Virology Specialty Laboratory (UW-VSL) (Seattle, Washington, USA)

Endpoint assay laboratories

- Duke University Medical Center (Durham, North Carolina, USA)
- Fred Hutch/University of Washington (Seattle, Washington, USA)

Study sites

HVTN Clinical Research Sites (HVTN CRSs) in the United States to be specified in the Site Announcement Memo

Safety monitoring

HVTN 133 PSRT; HVTN Safety Monitoring Board (SMB)

4.1 Rationale for trial concept

Elicitation of broadly neutralizing antibodies (bnAbs) against the HIV-1 envelope (Env) is likely to be central to a successful protective HIV-1 vaccine (4). There are multiple conserved sites on Env that are targets for bnAbs but no current vaccination regimens elicit these kinds of antibodies. A subset of chronically infected subjects make bnAbs, and this has allowed identification of several characteristics shared by all bnAbs (5).

One highly conserved and well-studied vaccine target in Env is gp41 near the viral membrane proximal external region (MPER) where several bnAbs bind (6). One of these bnAbs, 2F5, has been shown to protect against vaginal simian/human immunodeficiency virus (SHIV) transmission (7) when given passively suggesting that, if induced in sufficient titers, such bnAbs may be effective for prevention of HIV-1 infection. The MPER of gp41 is a highly conserved region, rich in aromatic residues, and its role in HIV-1 fusion is evident from studies showing that mutation of tryptophan residues in the MPER inhibits cell fusion and viral infectivity (8). However, MPER-specific bnAbs are rarely made in natural HIV-1 infection (9) and as yet are not made following HIV-1 envelope protein vaccination (10, 11).

Immunological tolerance mechanisms (12, 13), which cause profound clonal deletion of B cells expressing autoreactive bnAbs like 2F5 (14), have been postulated to limit induction of MPER gp41 bnAbs. Verkoczy and Haynes have recently demonstrated in mice that although most precursors of MPER bnAbs are deleted at the first tolerance checkpoint in bone marrow, a small population (5%) of bnAb precursors emigrate from the bone marrow and exist in peripheral immune organs as anergic B cells that can be activated by an appropriate immunogen to produce 2F5 bnAbs in plasma (15). These residual anergic clones are competent to undergo class-switching, activation and expansion in response to immunization resulting in potent serum IgG neutralizing responses. Thus, in principle, overcoming tolerance of self-reactive bnAb-expressing B cells by immunization is a feasible part of an antibody-based HIV-1 vaccine strategy.

Despite these data showing tolerance control of this class of antibodies, there are data that suggest it might be possible to elicit such antibodies by vaccination. While most individuals develop bnAbs only after several years of infection, Sather et al. described two HIV-1-infected persons who developed MPER-directed bnAb activity one year after infection (16) suggesting that it may be possible to develop MPER-directed bnAb activity relatively quickly compared with other bnAb epitopes (17). Rhesus macaques immunized using MPER peptides displayed on liposomes (described in Section 4.2) developed antibodies that recognized the 2F5-epitope (18, 19), and monoclonal antibodies isolated from these macaques demonstrated a maturation pattern similar to that of 2F5-including broad neutralization in an assay using TZM-bl cells that express CD64 (FcγR1)

(19). Thus, MPER peptide liposomes are an immunogen that have been shown to initiate the development of 2F5-like bnAb precursors in rhesus macaques, providing a rationale for the testing of this immunogen in human participants. This study will determine if 2F5-like bnAb precursors can be elicited in humans utilizing an MPER peptide thus opening the path to exploiting B cell lineage development as a mechanism to elicit bnAbs.

4.2 GTH1-656 MPER peptide liposome

Rationale for gp41 MPER peptide liposome immunogen design

Data suggest that MPER residues are oriented or presented differently on a lipid bi-layer compared to free peptides (20-22). MPER peptides alone as immunogens generally are ineffective for the induction of bnAbs (23). MPER peptides in micelles or in liposomes with membrane anchor tags are likely to be less flexible and more likely to adopt a relatively ordered conformation (20, 21). It has been shown that stable scaffold structures of MPER peptides can induce antibody responses that target the 2F5-bound peptide conformation (23). Studies using synthetic peptide-liposome conjugates have shown that membrane anchoring is important for the presentation of 2F5 epitope structure (24); the N and C termini of the gp41 MPER are differentially exposed on the membrane; and the stable docking of monoclonal antibodies (mAbs) 2F5 to peptide-liposomes is influenced by the extent of membrane immersion of the binding epitopes (21).

[figure not shown]

Figure 4-1 Design of the MPER peptide liposome

Figure 4-1 shows the general design of the MPER peptide-liposome. The MPER-656 liposomes immunogen includes the relevant gp41 MPER component and a

lipid component to induce membrane binding. The MPER-656 peptide sequence (⁶⁵⁶NEQELLELDKWASLWNWFNITNWLWYIK⁶⁸³) is derived from the membrane proximal region of HIV-1 gp41 and includes the core epitopes of the broadly neutralizing mAbs 2F5 (⁶⁶²ELDKWAS), 4E10 (⁶⁷¹NWFNIT), and 10E8 (⁶⁷¹NWF⁶⁷⁶T⁶⁸³K). The MPER-656 peptide was synthesized with a C-terminal hydrophobic membrane anchor tag (YKRWILGLNKIVRMYS) which facilitates anchoring of the peptide to synthetic liposomes and presentation of the optimal peptide conformation for MPER bnAb binding, while occluding the binding of non-neutralizing MPER antibodies (21, 24). The gp41 MPER-656 peptide liposome immunogen has been shown to be able to induce triggering of anergic 2F5 bnAb cells in 2F5 knock-in mice, resulting in high levels of plasma bnAb. MPER-656 peptide adjuvanted liposomes were constructed as described (21, 24, 25).

4.3 Alhydrogel[®] adjuvant

Alhydrogel[®] adjuvant, aluminum hydroxide (alum), is a commonly used vaccine adjuvant and will be administered with this peptide vaccine.

4.4 Trial design rationale

This study will evaluate the safety and immunogenicity of a novel gp41 MPER peptide-liposome vaccine in healthy HIV-1–uninfected adults. The study will evaluate 2 different dose levels of the vaccine (500 and 2,000 mcg) in a dose escalation trial. Safety and tolerability will be assessed after the first vaccination and safety parameters met before advancing to the higher dose level. Vaccination will be given by needle and syringe intramuscularly. Each dose will be split in two and given at 2 separate injection sites.

Preclinical testing of this and other HIV-1 vaccine candidates suggests that sequential immunization with immunogens, perhaps over a prolonged period of time, may be required to induce bnAb production. This vaccine will be given at 4 timepoints over a period of 12 months to determine the degree to which MPER-directed bnAb precursors can be elicited and matured by this vaccine candidate. Safety, tolerability, and immunogenicity data will be collected after each vaccination.

Preclinical trials have given up to 2 mg of peptide-liposome vaccine without significant toxicity. However, a human mAb targeting the epitope included in this vaccine has been shown to react with cardiolipin histones and centromere B autoantigens (26). Participants in this study will be monitored for vaccine-induced toxicities. This vaccine is designed to elicit 2F5-like bnAb precursors, and human trials of passive immunization with up to 5 grams of 2F5 antibody did not result in clinical prolongation of clotting times (activated partial thromboplastin time [aPTT], prothrombin time [PT] and dilute Russell's viper venom time [DRVVT]) and no binding to cardiolipin was seen in clinical samples. In human studies

administering combinations of mAbs 2F5, 4E10, and 2G12, slight rises in binding to phosphatidylserine and cardiolipin were seen in plasma along with a mild, transient prolongation of aPTT in 4/12 participants (27). Because of this possible autoreactivity, volunteers will be screened for pre-existing autoimmune disorders and safety labs will include evaluation of clotting times as well as induction of anti-cardiolipin antibody and anti-nuclear antibody. The full MPER neutralizing antibody (nAb) epitope, ELDKWA, is present in the host tryptophan catabolism pathway enzyme kynureninase (KYNU). It is not expected that antibodies against this enzyme will have clinically apparent adverse effects, and studies in mice and non-human primates (NHPs) have shown that immunization with MPER peptide liposome vaccine did not alter tryptophan metabolism (18).

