4.8 Clinical studies

4.8.1 Rationale for human trials

Preclinical trials have shown that immunization with HIV-1 MPER peptide-liposome vaccines can initiate bnAb lineages against HIV-1 gp41 (15) in mice and non-human primate models (25). The purpose of this trial will be to determine if MPER-directed bnAb precursors can be expanded in humans. The primary objective of this phase 1 study will be to determine the safety of the MPER peptide liposome vaccine in healthy adults. In previous studies with small animals (guinea pigs) an MPER peptide immunogen dose of 100 mcg per animal induced antibodies that bound to peptides that included the bnAb 2F5 epitope (25). A higher immunogen dose of 1 mg administered to NHP induced antibodies that mapped to the core (⁶⁶⁴DKW) 2F5 epitope and also bound avidly to the conformationally relevant gp41-inter and 2F5 scaffold proteins (25). Thus, in human vaccinees, we will evaluate doses of 0.5 mg and 2 mg of peptide in a dose escalation fashion. Preclinical trials utilizing doses as high as 2 mg peptide in liposomes have shown no adverse effects. This study will evaluate two doses over a longer period of time (4 immunizations over a 12-month period). Safety and

tolerability will continue to be the primary endpoints but immunogenicity, including binding antibody that maps to the 2F5-epitope, expansion of antibodies with characteristics of MPER-directed bnAb B-cell lineages, and evaluation of sera for the production of bnAbs will be important endpoints.

The MPER peptide included in the vaccine includes epitopes for both 2F5 and 4E10 bnAbs. Despite the inclusion of the 4E10 epitope, antibodies to this area of the peptide have not been elicited in any preclinical trials (15). This is felt to be due to the fact that the 4E10 epitope is located adjacent to the anchoring tag and thus is likely not well presented. For this reason, the immunological endpoints in this study will be directed to the 2F5-epitope. As noted in Section 4.4, some MPER bnAbs including 2F5 and 4E10 monoclonal antibodies (mAbs) have autoreactivity. The preclinical data presented above demonstrate that this immunogen does not elicit pathological antibodies supporting the safe use of the MPER-656 liposome vaccine in humans. We do not anticipate problems with those kinds of antibodies in this trial, but our monitoring plan is designed to capture those problems should they arise.

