7.1 Inclusion criteria

General and Demographic Criteria

1. **Age** of 18 to 50 years
2. **Access to a participating HVTN CRS** and willingness to be followed for the planned duration of the study
3. Ability and willingness to provide **informed consent**
4. **Assessment of understanding:** volunteer demonstrates understanding of this study; completes a questionnaire prior to first vaccination with verbal demonstration of understanding of all questionnaire items answered incorrectly
5. **Agrees not to enroll in another study** of an investigational research agent while in this study
6. **Good general health** as shown by medical history, physical exam, and screening laboratory tests

HIV-Related Criteria:

7. Willingness to receive **HIV test results**

8. Willingness to discuss HIV infection risks and amenable to **HIV risk reduction counseling**
9. Assessed by the clinic staff as being at “**low risk**” for **HIV infection** and committed to maintaining behavior consistent with low risk of HIV exposure through the last required protocol clinic visit (see [Appendix F](#))

Laboratory Inclusion Values

Hemogram/Complete blood count (CBC)

10. **Hemoglobin** ≥ 11.0 g/dL for volunteers who were assigned female sex at birth, ≥ 13.0 g/dL for volunteers who were assigned male sex at birth. For transgender participants who have been on hormone therapy for more than 6 consecutive months, determine hemoglobin eligibility based on the gender with which they identify (ie, a transgender female who has been on hormone therapy for more than 6 consecutive months should be assessed for eligibility using the hemoglobin parameters for persons assigned female sex at birth)
11. **White blood cell count** = 2,500 to 12,000 cells/mm³ with normal differential, or differential approved by Investigator of Record (IoR) as not clinically significant
12. **Total lymphocyte count** ≥ 650 cells/mm³ with normal differential, or differential approved by IoR as not clinically significant
13. **Remaining differential** either within institutional normal range or with site physician approval
14. **Platelets** = 125,000 to 550,000 cells/mm³

Chemistry

15. **Chemistry panel: alanine aminotransferase (ALT)** < 1.25 times the institutional upper limit of normal; creatinine ≤ 1.1 times the institutional upper limit of normal

Clotting and autoantibodies

16. **Anticardiolipin IgG antibodies** below the upper limit of normal
17. Negative **antinuclear antibodies**

Virology

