9.2 Pre-enrollment procedures

Screening may occur over the course of several contacts/visits, up to and including before vaccination on day 0. All inclusion and exclusion criteria must be assessed within 56 days before enrollment, unless otherwise specified in the eligibility criteria (or below in this section).

After the appropriate informed consent has been obtained and before enrollment, the following procedures are performed:

- Medical history, documented in the case history record
- Assessment of whether the volunteer is at low risk for HIV infection (see [Appendix G](#)).
- Complete physical examination, including height, weight, vital signs, and clinical assessments of head, ears, eyes, nose, and throat; neck; lymph nodes; heart; chest; abdomen; extremities; neurological function; and skin
- Assessment of concomitant medications the volunteer is taking, including prescription and nonprescription drugs, vitamins, topical products, alternative/complementary medicines (eg, herbal and health food supplements), recreational drugs, vaccinations, and allergy shots
- Laboratory tests, including:
 - Screening HIV test
 - HBsAg
 - Anti-HCV abs
 - Syphilis test
 - CBC with differential
 - Chemistry panel (ALT, AST, alkaline phosphatase, creatinine)

- Urine dipstick
 - Urine or serum pregnancy test (volunteers who were born female); Persons who are NOT of reproductive potential due to having undergone total hysterectomy or bilateral oophorectomy (verified by medical records), are not required to undergo pregnancy testing
 - Anticardiolipin IgG antibodies
 - Antinuclear antibodies
- Administration of behavioral risk assessment questionnaire
 - Obtaining of volunteer demographics in compliance with the NIH Policy on Reporting Race and Ethnicity Data: Subjects in Clinical Research, Aug. 8, 2001 (available at <http://grants.nih.gov/grants/guide/notice-files/NOT-OD-01-053.html>)
 - Counseling on HIV testing and risk reduction, performed in compliance with the US Centers for Disease Control and Prevention (CDC)'s current guidelines or other local guidelines for HIV counseling, testing, and referral as described in Section 9.6

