10.2 Total blood volume

Required blood volumes per visit are shown in [Appendix E](#). Not shown is any additional blood volume that would be required if a safety lab needs to be repeated, or if a serum pregnancy test needs to be performed. The additional blood volume would likely be minimal. The total blood volume drawn for each participant will not exceed 500 mL in any 56-day (8-week) period.

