Appendix E Laboratory procedures

Procedure	Ship to ¹	Assay Location ²	Tube ⁴	Tube size (vol. capacity) ⁴	Visit:	1	2	3	4	5	6	7	8	9	10	11	12	Total	
					Day:	Screening	D0	D14	D56	D70	D168	D182	D273	D364	D371	D378	D546		
					Month:	visit ³	M0	M0.5	M2	M2.5	M6	M6.5	M9	M12	M12.25	M12.5	M18		
						VAC1		VAC2		VAC3				VAC4					
						MPER or Placebo		MPER or Placebo		MPER or Placebo				MPER or Placebo					
BLOOD COLLECTION																			
Screening or diagnostic assays																			
Screening HIV test	Local lab	Local lab	SST	5mL	5	—	—	—	—	—	—	—	—	—	—	—	—	5	
HBsAg/anti-HCV	Local lab	Local lab	SST	5mL	5	—	—	—	—	—	—	—	—	—	—	—	—	5	
Syphilis	Local lab	Local lab	SST	5mL	5	—	—	—	—	—	—	—	—	—	—	—	—	5	
Anticardiolipin antibodies (ACA), IgG	Local lab	Local lab	SST	5mL	5	—	—	—	—	—	—	—	—	—	—	—	—	5	
Antinuclear antibodies (ANA)	Local lab	Local lab	SST	5mL	5	—	—	—	—	—	—	—	—	—	—	—	—	5	
HIV diagnostics ⁹	UW-VSL	UW-VSL	EDTA	10mL	—	—	—	—	—	10	10	—	10	10	—	—	20	60	
Safety labs ¹⁰																			
CBC/Diff/Platelets	Local lab	Local lab	EDTA	5mL	5	—	5	—	5	—	5	—	—	—	—	5	—	25	
Chemistry panel ⁵	Local lab	Local lab	SST	5mL	5	—	5	—	5	—	5	—	—	—	—	5	—	25	
Autoantibody assays																			
Antinuclear antibodies (ANA)	CSR	Non-HVTN Labs at Duke-DHVI	SST	8.5mL	—	y	y	—	y	—	y	—	—	—	—	y	y	0.0	
Anticardiolipin antibodies (ACA), IgG	CSR	Non-HVTN Labs at Duke-DHVI	SST	8.5mL	—	y	y	—	y	—	y	—	—	—	—	y	y	0.0	
Host genetics ⁷	CSR	HVTN Labs	ACD	8.5mL	—	17	—	—	—	—	—	—	—	—	—	—	—	17	
Immunogenicity assays ⁶																			
Humoral assays																			
HIV-1 binding Ab	CSR	HVTN Labs	SST	8.5mL	—	8.5	8.5	—	8.5	—	8.5	—	—	—	—	8.5	8.5	51	
Lipid binding Ab	CSR	HVTN Labs	SST	8.5mL	—	y	y	—	y	—	y	—	—	—	—	y	y	0	
Ab avidity	CSR	HVTN Labs	SST	8.5mL	—	y	y	—	y	—	y	—	—	—	—	y	y	0	
Neutralizing Ab	CSR	HVTN Labs	SST	8.5mL	—	8.5	8.5	—	8.5	—	8.5	—	—	—	—	8.5	8.5	51	
Cellular assays																			
HIV-specific ICS	CSR	HVTN Labs	ACD	8.5mL	—	—	—	—	42.5	—	42.5	—	—	—	—	42.5	42.5	170	
Phenotyping (pTfh)	CSR	HVTN Labs	ACD	8.5mL	—	42.5	—	—	—	—	—	—	—	42.5	42.5	—	42.5	170	
Ag-specific B-cell phenotyping	CSR	HVTN Labs	ACD	8.5mL	—	42.5	42.5	—	42.5	—	42.5	—	—	—	42.5	42.5	42.5	297.5	
B-cell lineage	CSR	HVTN Labs	ACD	8.5mL	—	34	34	—	34	—	34	—	—	—	34	34	34	238	
Specimen storage																			
PBMC	CSR		ACD	8.5mL	—	51	51	—	85	—	85	—	—	—	25.5	85	85	467.5	
Serum	CSR		SST	8.5mL	—	17	17	—	17	—	17	—	—	8.5	—	17	17	110.5	
Visit total					35	221.0	172	0	258.0	10	248.0	10	61	145	248.0	301	1707.5		

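### Section 4.4 promises clotting times among the safety labs, but no clotting test appears in the protocol's eligibility criteria, laboratory lists or Appendix E schedule

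*Combined protocol and SAP*

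**What the plan says.** Section 4.4 spells out clotting times as aPTT, PT and DRVVT. It reports that up to 5 g of 2F5 alone caused no clinical prolongation, and that a mild, transient aPTT prolongation was seen in 4 of 12 recipients of combinations of 2F5, 4E10 and 2G12. It then commits: "safety labs will include evaluation of clotting times as well as induction of anti-cardiolipin antibody and anti-nuclear antibody". Section 4.8.1 returns to autoreactive antibodies and says "our monitoring plan is designed to capture those problems should they arise".

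The sections that would put this into practice read as follows:

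- **7.1** has a heading "Clotting and autoantibodies". Only criteria 16 (anticardiolipin IgG) and 17 (ANA) stand under it.
- **9.2** lists the screening tests, including "Chemistry panel (ALT, AST, alkaline phosphatase, creatinine"), ACA and ANA. It has no clotting test.
- **9.4 and 9.11** list follow-up and early-termination tests without a clotting test. Both lists are introduced as open ones.
- **Appendix E**, safety labs block, has two rows: "CBC/Diff/Platelets" and a chemistry panel. A row for "Anticardiolipin antibodies (ACA), IgG" appears twice in the appendix, once at screening and once for later visits. There is no clotting row.
- **10.2** refers to Appendix E for required blood volumes. It excepts only repeats and serum pregnancy tests: "Not shown is any additional blood volume that would be required if a safety lab needs to be repeated".

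Section 13 lists only version 1.0, so superseded text does not explain the difference.

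**The concern.** Section 4.4 makes three laboratory commitments for one stated reason, and the schedule carries out two of them. A reader of 4.4 and 4.8.1, such as an ethics committee, would take it that clotting is monitored. A site that follows Appendix E would collect no clotting result.

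Laboratory measures of safety are part of primary endpoint 1, and 6.4.3.3 plans changes from baseline for local laboratory values. For clotting there would be no baseline and no later value. The PSRT's review of Group 1 through two weeks after the first dose would have no scheduled clotting data. The 7.3.3 rule on related grade 3 laboratory abnormalities could act only on a test ordered for clinical reasons.

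The later draws matter at least as much as D14. Section 4.7.1.4 describes antibodies to the 2F5 epitope in macaques after more than one immunization, although the rabbits in 4.7.1.6 responded after one.

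**Working it through.** **1. Commitment against schedule**

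| Place | ACA | ANA | Clotting time |
|---|---|---|---|
| 4.4 (commitment) | yes | yes | yes |
| 7.1 | yes | yes | in the heading only |
| 9.2 | yes | yes | no |
| 9.4 (open list) | not named | not named | no |
| 9.11 (open list) | yes | yes | no |
| Appendix E | yes | yes | no |

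Appendix E lists ACA and ANA at screening (local lab) and at six later visits (D0, D14, D70, D182, D378, D546). The six later entries are assays on stored serum at a non-local laboratory, outside the safety labs block. Clotting tests are listed at 0 of 12 clinic visits.

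**2. Is there an unlisted tube?** Row totals printed in Appendix E (mL): five screening tests 5 × 5 = 25; HIV diagnostics 60; CBC 25; chemistry 25; host genetics 17; binding antibody 51; neutralizing antibody 51; ICS 170; pTfh 170; B-cell phenotyping 297.5; B-cell lineage 238; stored PBMC 467.5; stored serum 110.5.

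25 + 60 + 25 + 25 + 17 + 51 + 51 + 170 + 170 + 297.5 + 238 + 467.5 + 110.5 = **1707.5 mL**, the printed total.

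By visit, the rows give 35 (screening), 221 (D0), 171.5 (D14), 0 (D56), 258 (D70), 10 (D168), 248 (D182), 10 (D273), 61 (D364), 144.5 (D371), 248 (D378) and 300.5 (D546). These match the printed visit totals after rounding. The HIV diagnostics columns are shifted in the text used here. They were placed by the visit totals and agree with the HIV assessment visits in Appendix F. No volume is left over for a separate clotting tube.

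**3. Would a clotting tube fit?** Assume a tube of at most 5 mL at screening, D14, D70, D182 and D378.

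- Per participant: 5 × 5 = 25 mL; 1707.5 + 25 = 1732.5 mL; 25 / 1707.5 = 1.5%.
- 56-day totals on target days, before and after: D14 427.5 to 437.5; D70 429.5 to 439.5; D182 258 to 263; D378 (61 + 144.5 + 248) 453.5 to 458.5.
- Worst case in the Appendix I windows, using the lower target day where the lower allowable day is blank: the D273 visit on day 273 + 28 = 301 and the D364 visit on day 364 − 28 = 336. The next two visits then fall on days 343 and 350, so all four lie within 49 days. Volume: 10 + 61 + 144.5 + 248 = 463.5 mL, or **468.5 mL** with the added tube.
- Margin under the 500 mL cap: 500 − 468.5 = 31.5 mL, or six 5 mL repeat tubes.

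**4. Repeat tests.** 24 participants × 5 draws × 2 tests (PT, aPTT) = 240 results. If 1% to 5% are abnormal by chance (an assumption; the documents give no rate): 240 × 0.01 = 2.4 and 240 × 0.05 = 12. This is a floor. Screening tests would also be run on volunteers who are not enrolled, and the protocol does not say how many will be screened.

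**The case against.** **The test may be specified elsewhere.** Section 9 refers to Appendix D as well as Appendix F for procedures, and 10.1 says the Site Lab Instructions and SSP cover screening and safety testing. Appendix D and those two documents were not available for this check. This stands as a limit on scope. A reader might infer that no clotting test will be done in the trial; the documents support only that the available protocol text does not schedule one.

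**A balanced blood volume does not prove that no test is run.** Appendix E has zero-volume rows that draw on stored serum. This is right, and the missing row is the main evidence. The footnote on shared serum names autoantibody, avidity and lipid-binding assays, and not clotting.

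**Other monitoring covers the risk.** Platelets are counted, ACA is assayed, exclusion 28 removes known bleeding disorders, and clinical events would be reported as AEs or AESIs. None of these measures a clotting time. The later ACA assays are also not local safety labs, and no turnaround to the PSRT is stated.

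**The consequences are small.** No pause, stopping or escalation criterion names clotting, and 6.4.3.3 does not name it among the local laboratory values. A reader might infer that primary endpoint 1 is incomplete or that participants face a known hazard. The text supports neither. Prolongation followed combinations that included 4E10, 2F5 alone caused none clinically, and 4E10-like antibodies were not detected in the macaque studies (4.6.1.2, 4.6.2).

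**The sentence in 4.4 may be leftover text.** Four lists and the schedule omit clotting, which fits this at least as well as a forgotten test. The documents do not settle which it is, so removing the commitment must remain open as a remedy.

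**Conclusion.** The inconsistency is real and should be corrected. Section 4.4 states a safety measure that 7.1, 9.2, 9.4, 9.11 and Appendix E do not deliver. The finding rests mainly on 4.4, 7.1, 9.2 and Appendix E, because 9.4 and 9.11 are open lists. Its size is zero scheduled clotting results over 12 clinic visits, with no baseline, while the two companion antibody tests appear at screening and six later visits.

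The clinical risk appears low, so this is a gap between commitment and schedule rather than evidence of harm. It might be inferred from the 7.1 heading that a clotting threshold was meant for eligibility. Section 4.4 promises evaluation in the safety labs and no entry threshold, so one stray heading word does not establish that. The feasibility figures rest on the assumed tube size and the reading of blank window limits given above; the repeat-test range rests on the assumed 1% to 5% rate.

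**What to change.** One amendment, by either route.

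**Add the test.** Put local PT/aPTT into Appendix E, 9.2, 9.4 and 9.11, at baseline and at the existing D14, D70, D182 and D378 draws. State whether DRVVT, which 4.4 also names, is intentionally omitted. Baseline can be screening or D0 before vaccination:

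- Screening already has a local CBC and chemistry draw, as do the four later visits, but every volunteer screened would be tested.
- D0 limits testing to participants about to be enrolled, but Appendix E has no local blood draw that day, and Appendix F does not require such results before vaccination.

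The cost is at most 25 mL per participant with no new visit, and at least 2 to 12 repeat tests on the stated assumption (more if screen failures are tested). A clotting criterion in 7.1 is optional. If wanted, it could follow the allowance in criterion 11, "differential approved by Investigator of Record (IoR) as not clinically significant", applied to PT and aPTT. Any resulting screen failures or approvals would be a further cost, not estimated here.

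**Remove the commitment.** If the sponsor's clinicians judge testing unnecessary, delete clotting times from the safety-lab sentence in 4.4 and the word Clotting from the 7.1 heading, and give the reason. The cost is text only.
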